9.6.3 Observation Period (Extended Screening Weeks 1-12)

Only patients with Visit 1a Worst itch NRS score of less than 5 (<5) (Visit 1a for these patients is considered OV1) should enter the Observation Period, which includes subsequent study visits OV 2-4 at approximately one month intervals over the next 12 extended screening weeks (See [Table 7](#)). While patients remain in the Observation Period, they will not be considered enrolled into the study, but as participating in an extended screening process until they are eligible for enrollment. Patients evaluated at OV 2-4 and who record Worst itch NRS greater than or equal to 5 (≥ 5), and are otherwise eligible, can immediately begin Visit 1b and transition into the Treatment Period.

For these patients, the sum of time in the Observation Period and Treatment Period will not exceed 50 weeks. As a result, both the Observation Period and Treatment Period will differ in length for different patients. To ensure that the total number of study weeks does not exceed 50 weeks, that all patients complete proper titration of study drug up to the assessment of TV 2 during Treatment Week 3, and that the final Treatment Period visit is always TV14, see [Table 8](#) for visit details. As such, visits during this period are not equivalent to Treatment Weeks. During the Observation Period, patients are participating in Extended Screening Weeks.

9.6.3.1 *Observation Visit 2 at Extended Screening Week 4 and Observation Visit 3 at Extended Screening Week 8*

The following procedures are to take place at this visit:

- administer the Worst itch NRS
 - If the Worst Itch NRS is less than 5 (<5), perform the following Observation Visit procedures at any time during the visit
 - obtain vital signs
 - record AEs
 - record concomitant medications
 - If the Worst Itch NRS is greater than or equal to 5 (≥ 5), transition the patient to the Treatment Period and conduct Visit 1b procedures (described in [Section 9.6.4](#)) on the same day as this visit. See [Table 8](#) for a summary related to future Treatment Period Visits.

9.6.3.2 *Observation Visit 4 at Extended Screening Week 12*

The following procedures are to take place at this visit:

- administer the Worst itch NRS
 - If Worst Itch NRS is less than 5 (<5), perform the following Observation Visit procedures at any time during the visit
 - obtain vital signs
 - administer the following
 - Average itch intensity NRS
 - VRS
 - ItchyQoL
 - MOS Sleep-R
 - HADS
 - record AEs
 - record concomitant medications
 - If the Worst Itch NRS is greater than or equal to 5 (≥ 5), transition the patient to the Treatment Period and conduct Visit 1b procedures (described in [Section 9.6.4](#)) on the same day as this visit. See [Table 8](#) for a summary related to future Treatment Period Visits.

Patients whose Worst Itch NRS is less than 5 (<5) at the OV4 should be screen failed from the study. No Washout/Safety follow-up visit is to take place.

9.6.3.3 *Transitioning from the Observation Period to the Treatment Period*

- For patients who have a Worst NRS score that is greater than or equal to 5 (≥ 5) at Observation Visit 2, 3, or 4, complete Visit 1b procedures (see [Section 9.6.4](#)).
- These patients will receive up to 46 weeks of study medication treatment.
- See [Table 8](#) for the Treatment Period Visits to be completed post Visit 1b, as well as the number of weeks of study drug to dispense at each Treatment Visit and when to schedule the End of Treatment Visit 14, TV14, to take place.
- See [Section 9.6.2](#) and the Schedule of Events ([Appendix 1](#)) for procedures to be performed at each applicable Treatment Visit.

9.6.4 Transition to Treatment Period (Visit 1b)

Confirm each patient's eligibility (see [Sections 8.2](#) and [8.3](#)) prior to performing any Visit 1b procedures. If the patient does not meet eligibility requirements, do not perform any Visit 1b procedures; the patient is to be screen failed.

See [Table 4](#) for summary of Visit 1b procedures.

Patients evaluated at OV 2-4 who record a Worst itch NRS greater than or equal to 5 (≥ 5) and, are otherwise eligible, can immediately begin Visit 1b. This patient then transitions into the Treatment Period and will undergo the following procedures:

- obtain vital signs
- conduct a physical examination
- collect central laboratory samples (hematology and chemistry)

- collect serum pregnancy sample in women of childbearing potential (done at the central laboratory)*
- collect urine for central lab urinalysis
- urine for pregnancy (must be confirmed negative prior to dispensing study drug)*

* If the urine pregnancy test result is negative and the serum pregnancy test result is positive, the patient is to be contacted and the following actions are to take place:

- instruct the patient to discontinue taking study drug
- schedule the patient for an unscheduled visit to collect another serum pregnancy test

The serum pregnancy test result will be used to determine the patient's eligibility to continue receiving study treatment. See [section 17.5.2.1](#) regarding how pregnancies are to be handled in this study.

- obtain blood for PK
- Perform 12-Lead ECG after at least 5 minutes in a supine position (See the Study Reference Manual for ECG procedures, [section 17.4](#) Electrocardiograms for the handling of Cardiovascular adverse events)
- administer PRO measurements:
 - Average itch intensity NRS
 - VRS
 - ItchyQoL
 - MOS Sleep-R
 - HADS
 - PBI-P

The PRO questionnaires must be administered at the study site under the supervision of and by trained study staff, strictly adhering to PRO Administration Instructions (see Study Reference Manual).

- record AEs
- review of concomitant medications, including over-the-counter medications, nutritional supplements, and vitamins
- complete the PAS
- dispense Study Drug to the patient required until return at Treatment Visit 2, TV2
- instruct patients to self-administer the first dose on the evening of Visit 1b at home
- instruct patients to notify the Investigator if any significant CNS AEs occur, and not to drive or operate dangerous machinery until the effect of the Study Drug can be assessed by the Investigator, see [Section 9.3](#)
- all patients should be instructed to titrate to their most tolerated dose. See [Table 3](#) Drug Dosing Schedule for more information. Here is the recommended Week 1 titration schedule for patients who tolerate study drug:
 - Day 1 (the first day that study drug is dispensed to a patient on treatment): No dose in the AM and 30 mg in the PM
 - Day 2: No dose in the AM and 30 mg in the PM
 - Day 3: 30 mg in the AM and 30 mg in the PM

Day 4: 30 mg in the AM and 30 mg in the PM

Day 5: 30 mg in the AM and 60 mg in the PM

Day 6: 60 mg in the AM and 60 mg in the PM

Day 7: 60 mg in the AM and 60 mg in the PM

- Instruct patients to bring all remaining Study Drug to the dialysis unit for each subsequent treatment period study visits.
- If a patient misses 3 or more consecutive doses, contact the Medical Monitor.

The next study visit will be Treatment Visit 2 (TV2). However, to ensure that the total number of study weeks does not exceed 50 weeks, that all patients complete proper titration of study drug and that the End of Treatment Visit is always TV14, see [Table 8](#) for more information.

The next visit will be Treatment Visit 2 ([Section 9.6.2.1.2](#)). See [Appendix 1](#), Schedule of Event and [Table 8](#) for the Treatment Visit Schedule for Patients Entering Treatment via Visit 1b.

9.6.5 Washout and Safety Follow-Up Period

All patients who received Treatment, but did not withdraw consent, will have a 2-week Washout and Safety Follow-Up Period following TV14. During this visit, the PRO questionnaires must be administered at the study site under the supervision of and by trained study staff, strictly adhering to PRO Administration Instructions (see Study Reference Manual). Please see the Schedule of Events in [Appendix 1](#) for details of the Washout and Safety Follow-Up Period assessments. Additional information for this visit is provided below.

For patients who entered the Treatment Period at Visit 1a, the Washout and Safety Follow-Up Period Visit would take place during week 53, post TV14. However, for a patient who enters the Treatment Period at Visit 1b, the Washout and Safety Follow-up Period Visit will take place 14 days (plus the visit window) post TV14.

For patients who met Failure-to-Improve criteria or who discontinue treatment for other reasons (see [Section 11.1](#)), this visit is to take place 14 days (+ 7 days) after TV14.

The following procedures are to take place at this visit:

- obtain vital signs
- perform 12-Lead ECG after at least 5 minutes in a supine position (See the Study Reference Manual for ECG procedures, [section 17.4](#) Electrocardiograms for the handling of Cardiovascular adverse events)
- perform brief neurological assessment
- collect blood for central laboratory measurements and PK
- administer PRO measurements:
 - Worst itch NRS
 - Average itch intensity NRS
 - VRS
 - ItchyQoL

- MOS Sleep-R
- HADS

The PRO questionnaires must be administered at the study site under the supervision of and by trained study staff, strictly adhering to PRO Administration Instructions (see Study Reference Manual).

- AEs and concomitant medications (including rescue medications) will be recorded
- collect the Rescue Medication Log will be collected from the patient at this visit
- retrieve any remaining study drug not previously returned by the patient
- retrieve the 14 day SOWS packet

For patients who prematurely discontinued study medication for reasons other than withdrawal of consent, schedule the Premature Discontinuation of Study Drug Follow-up Telephone Contact visit.

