Treatment Period	
For patient directly entering the Treatment Period as of Visit 1a, the Treatment Period begins with Study Week 1 (Visit 1a) and ends with Study Week 50
 
For patients entering the Treatment Period after being followed in the Observation Period, the number of weeks on treatment and the end of the Treatment Period varies; Table 8 calculates the Treatment Visit assignments for any patient entering the Treatment Period from the respective Observation Period visits.
 
The End of Treatment Visit will take place after the patient completes the last week of study drug.
	Up to 50 weeks
Washout and Safety Follow-Up Period	
The Washout and Safety Follow-up Period is two (2) weeks in duration.
 
For patients directly entering the Treatment Period as of Visit 1a and completing 50 weeks of study drug treatment, the Washout and Safety Follow-up Period should take place during weeks 51 and 52.
 
For patients entering the Treatment Period after being followed in the Observation Period, the number of weeks on treatment and the end of the Treatment Period varies; Table 8 calculates the Treatment Visit assignments for any patient entering the Treatment Period from the respective Observation Period visits. The Washout and Safety Follow-up Period will take place during the two (2) weeks after the patients completes the last week of study drug.
 
The Washout and Safety Follow-up Period Visit will take place in the week following the completion of the two (2) week Washout and Safety Follow-up Period.
	2 weeks

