9.6 STUDY PROCEDURES

Before the initiation of study-specific procedures the patient must be given a complete explanation of the purpose of the study, evaluations to be conducted, and risks/benefits for study participation. Patients must understand the requirements of the study, provide informed consent (See [Section 9.6.1](#) and [Section 20.3](#)), agree to the study restrictions, and agree to return for the required assessments. After review of the informed consent is documented, the patient must give witnessed verbal and written consent. For this study, patients will retain their study number from study TR03.

With the exception of Visits 1a and 1b, windows for all visits will be +/-3 Days. Please see the Schedule of Events in [Appendix 1](#) for details of the Titration Period assessments and the Study Schematics Flow Charts in [Appendix 2](#). See [Section 9.7.1](#) for details of Study Drug Dosing and [Section 9.7.6.4](#) for information on the use of pre-medications with the Study Drug. Visit 6 of TR03 will serve as TR03ext Visit 1a.

Visit 1a has procedures to be done as summarized in [Section 9.6.1](#) regardless of the patient's pruritus intensity score. Following a set of common procedures, only patients who qualify for the Treatment Period based on meeting the pruritus intensity criteria will be eligible to receive study drug; Visit 1a corresponds to TV1. For patients who, during the final visit of TR03, did not meet the pruritus intensity criteria to enter the TR03ext Treatment Period, Visit 1a corresponds to OV1, the first visit of the Observation Period. If during a subsequent observation period visit to the site, the patient meets the pruritus intensity criteria, then that observation visit immediately transitions into Visit 1b (it also corresponds to TV1 since it is now the first Treatment Period visit) – See [Section 9.6.3.3](#) and [Section 9.6.4](#).

For subjects who transition to the Treatment Period from the Observation Period, [Table 8](#) provides details on the treatment visit schedule based on the study week that the subject transitioned from the Observation Period to the Treatment Period. The subject will follow the Treatment Visit schedule outlined on the Schedule of Events ([Appendix 1](#)).

For clarity,

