9.6.2.2.12 TV 14 (End of Treatment Visit)

This visit applies to all patients who completed TV13; including patients who met Failure-to-Improve criteria at any Treatment Visit during the study.

For patients who DID NOT meet Failure-to-Improve criteria during the conduct of the study, this visit (TV14) takes place after the patient has completed study medication.

- For patients who entered the Treatment Period at Visit 1a, TV14 would take place during week 51; four (4) weeks after TV13, as these patients should complete 50 weeks of treatment prior to TV14
- For patients who entered the Treatment Period at Visit 1b see [Table 8](#) for information on when TV14 is to take place

The following procedures are to take place at this visit:

- obtain vital signs
- perform physical examination
- perform brief neurological assessment
- complete the PAS
- perform 12-lead ECG after at least 5 minutes in a supine position (See the Study Reference Manual for ECG procedures, [section 17.4](#) Electrocardiograms for the handling of Cardiovascular adverse events)
- collect blood for central laboratory (hematology and chemistry) and serum pregnancy test for central laboratory
- collect urine for urinalysis at the central laboratory
- collect blood for PK
- at select sites only, perform skin biopsy (optional). Obtain 3 samples (i.e., H&E, nerve fiber density (histology) and MOR/KOR density (histology, Western Blot)); see the Lab and Study Reference Manuals for details
- administer PRO measurements:
 - Worst itch NRS
 - Average itch intensity NRS
 - VRS
 - ItchyQoL
 - MOS Sleep-R
 - HADS
 - SOWS

The PRO questionnaires must be administered at the study site under the supervision of and by trained study staff, strictly adhering to PRO Administration Instructions (see Study Reference Manual).

- record AEs

- review of concomitant medications, including over-the-counter medications, nutritional supplements, and vitamins
- perform study drug accountability, final retrieval of any dispensed study drug
- retrieve the Dosing Diary
- Dispense the 14 Day SOWS packet, instruct the patient on how to complete the scales and to complete the scales daily for 14 days
- Schedule the patient for the Washout and Safety Follow-up Period Visit

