9.7.8 Safety Assessments

As summarized in Section 6.2.7 of the Investigator Brochure, the CNS has been identified as the only target organ when nalbuphine was given to animals at high doses. In addition, the most frequently reported adverse events reported in the nalbuphine HCl ER tablet dosing studies were primarily in the nervous system and gastrointestinal organ system

categories. In order to monitor any potential CNS related side effects, a brief neurological assessment will be conducted at each study visit as well as a focused neurological medical history will be obtained at screening.

Safety will be determined by evaluation of the following:

- AEs
- Vital signs including weight, BP, heart rate (HR), respiratory rate (RR), and body temperature
- Physical examination
- Clinical laboratory data (see [Appendix 3](#) for list of analytes)
- Investigator reviewed ECG and central cardiac core laboratory read 12 Lead-ECG, cardiovascular grading, and/or cardiovascular related prohibited medications
- Subjective Opiate Withdrawal Scale (SOWS)

The SOWS is a self-administered scale for grading opioid withdrawal symptoms. It contains 16 symptoms whose intensity the patient rates on a scale of 0 (“not at all”) to 4 (“extremely”). The instrument can be found in [Appendix 4](#). In this study, patients will complete SOWS daily, starting at TV14, End of Treatment Visit through to the Washout and Safety Follow-up Period Visit. The SOWS will also be completed at the Early Termination Visit. As with all subjects who are discontinued from study drug, the patient will complete a daily SOWS scale for the two weeks following the last dose of study drug. The SOWS is a self-administered scale for grading opioid withdrawal symptoms. If the subject is experiencing any symptoms on the SOW scale to a moderate degree, the subject will be instructed to contact the site. If a subject is determined to be experiencing significant subjective withdrawal symptoms (at the Investigator’s discretion), the subject will be offered treatment.

The following will be used to assess patient eligibility to continue participation if the patient experiences CHF, angina pectoris and/or other cardiovascular exclusion criteria (see [Section 8.3](#) for the Exclusion Criteria and [Appendix 5](#) for the grading scales)

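### Protocol Version 2.0 gives conflicting timings for the washout visit and for the start and length of the SOWS, so the withdrawal record can be cut short or begin late

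*Protocol*

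**What the plan says.** All references are to protocol Version 2.0.

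**Washout visit**
- Section 9.6: "With the exception of Visits 1a and 1b, windows for all visits will be +/-3 Days".
- Section 9.6.5 says that treated patients who have not withdrawn consent "will have a 2-week Washout and Safety Follow-Up Period following TV14", then gives three rules. For Visit 1a entrants the "Follow-Up Period Visit would take place during week 53, post TV14". For Visit 1b entrants it comes fourteen days after TV14 with the visit window added. For patients who meet the failure-to-improve criteria or stop for other reasons, "this visit is to take place 14 days (+ 7 days) after TV14".
- Section 9.5, Table 2, without naming a group: the "Visit will take place in the week following the completion of the two (2) week Washout and Safety Follow-up Period".

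**SOWS**
- Section 9.6.2.2.12 (TV14): patients receive a 14-day packet and are told "to complete the scales daily for 14 days".
- Section 9.7.8: the scale is completed daily "starting at TV14, End of Treatment Visit through to the Washout and Safety Follow-up Period Visit". The same paragraph, like section 9.3, also gives a duration of two weeks counted from the last dose.
- Section 9.6.5: the packet is retrieved at the washout visit.

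**TV14 itself**
- Sections 9.6.2.2.1 to 9.6.2.2.11: patients who meet the failure-to-improve criteria stop drug and have TV14 procedures at that visit.
- Section 9.6.2.2.12: for Visit 1a completers TV14 falls in week 51, after 50 weeks of drug.

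**The concern.** Section 5.2 lists two secondary endpoints that rest on this period: changes in the patient-reported measures during washout, and daily changes in the SOWS. The SOWS is also a listed safety assessment, and a symptom of moderate degree is meant to prompt the patient to contact the site. An endpoint built on daily change needs one start day and one length. Here both depend on which section a site follows.

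Two consequences matter. A site can comply with section 9.6.5 and still collect the packet before it is finished. And if the first form is filled in at TV14, patients whose TV14 comes some days after the last dose have no record of their first days without drug, which belong to the washout that the endpoint names. With at most 60 patients and no formal testing, the descriptive summaries are all the reader will have.

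**Working it through.** The plan states no figure for this, so the check is a day count.

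**Inputs and conventions.** Week *w* covers treatment days 7(*w* − 1) + 1 to 7*w*. A Visit 1a completer is assumed to take the last dose at the end of week 50, day 7 × 50 = 350.

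**Visit 1a completers**
- TV14 in week 51: days 351–357, or 1–7 days after the last dose.
- Washout visit in week 53: days 365–371, or 365 − 350 = 15 to 371 − 350 = 21 days off drug.
- Gap from TV14 to the washout visit: 365 − 357 = 8 to 371 − 351 = 20 days.
- Section 9.6.2.2.12 also puts TV14 four weeks after TV13. TV13 is in week 46 (days 316–322), and adding 28 gives days 344–350, which is week 50. That section therefore disagrees with itself by a week.

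**Visit 1b entrants**
- 14 ± 3 = days 11–17 after TV14. If the added window means later only, 14 to 14 + 3 = days 14–17.
- If TV14 is on the last-dose day, off-drug time at the visit is 11–17 days. If TV14 is 7 days later, it is 18–24 days. The 0–7 day lag is an assumption.

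**Failure-to-improve patients**
- TV14 is the stopping visit, so 14 to 14 + 7 = 14–21 days off drug.

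**Table 2**
- The week after a 14-day washout is days 15–21. A Visit 1b entrant seen on day 12 satisfies section 9.6.5 read with the ±3-day rule and breaks Table 2.

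**SOWS forms if completed through to the washout visit (both end days counted)**

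| Group | Days from TV14 to visit | Forms | Forms in packet |
|---|---|---|---|
| Failure-to-improve | 14–21 | 15–22 | 14 |
| Visit 1b entrants (±3) | 11–17 | 12–18 | 14 |
| Visit 1a completers | 8–20 | 9–21 | 14 |

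The packet can be too short for the rule in section 9.7.8, and in the last two rows it can also be collected with forms outstanding.

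**Off-drug days covered by 14 forms starting at TV14**
- Lag 0 (failure-to-improve): off-drug days 0–13.
- Lag 1 (earliest Visit 1a completer): days 1–14.
- Lag 7 (latest Visit 1a completer): days 7–20, so 8 of off-drug days 1–14 are covered and days 1–6 are not.

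**The case against.** The three rules in section 9.6.5 are written for three groups, so they are not contradictions among themselves. That stands: the direct conflicts are with Table 2 and among the SOWS definitions. Next, the Visit 1b rule may mean later only, in which case no Visit 1b visit precedes day 14. That also stands as a possible reading, but section 9.6 defines the window with a minus side, and the 8–20 day gap for Visit 1a completers permits early collection without using that window at all.

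Most places agree on two weeks of SOWS, and the packet holds 14 forms. True, but they disagree on the start day, and section 9.7.8 gives two different durations in one paragraph. The last-dose wording is phrased for patients taken off drug, so its reach to completers is not certain; that is itself something to settle.

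A reader might infer that early stoppers are in general followed longer off drug than completers, so that a difference in rebound between the two groups would be an artefact. The documents do not support this. Visit 1a completers are seen 15–21 days after the end of week 50, against 14–21 days for failure-to-improve patients. A shorter time arises only for Visit 1b entrants under one reading of their window, and it can reverse if their TV14 lags the last dose. No comparison of rebound between completers and early stoppers is specified either. A share of forms lost cannot be stated, because that needs the spread of visit days, which the protocol does not give.

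The appendix tables of Version 2.0, to which section 9.6.5 refers, were not available for this check. They may state a window, but they could not remove conflicts within the body text.

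**Conclusion.** The point holds as an inconsistency in visit timing and in the SOWS definition. Depending on the section and the group, the washout visit falls 8–20, 11–17 (or 14–17) or 14–21 days after TV14, or in the week after the two-week washout. The SOWS has three definitions that differ in length or start day.

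In the extreme permitted case for a Visit 1a completer (TV14 on the last day of week 51, washout visit on the first day of week 53), at most 9 of 14 forms exist when the packet is collected, and the first six days off drug are unrecorded. These are limits of what the text allows, not forecasts. They rest on a last dose at the end of week 50 and on the first form being completed on the TV14 day.

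The endpoints are secondary and descriptive, so the damage is to interpretation and completeness, not to an error rate. The correction is cheap enough to be worth making.

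**What to change.** Reconcile Table 2 and sections 9.6, 9.6.2.2.12, 9.6.5 and 9.7.8, and check the Version 2.0 appendix tables at the same time:

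1. Exempt the washout visit from the minus side of the ±3-day window, so that it never takes place before the 14 SOWS days are complete. Set an upper limit consistent with the 53-week maximum. A window of 14–21 days after TV14 for everyone would not do: with TV14 on day 357 it reaches 357 + 21 = 378, past day 53 × 7 = 371.
2. Set one SOWS length, 14 daily forms, and one start, the last dose, as sections 9.3 and 9.7.8 already word it. For a Visit 1a completer the forms then cover days 351–364 and the week-53 visit (days 365–371) follows them, in line with Table 2. Completers must be given the packet before TV14. Remove the instruction to continue until the washout visit.
3. Record the last-dose date and summarise the SOWS by day since last dose.
4. Settle whether TV14 for Visit 1a completers is in week 51 or four weeks after TV13.

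The cost is amendment wording and one added date if it is not already captured; no visits or forms are added. Patients lose the option of an early washout visit, and completers handle the packet earlier, so they need clear instruction on when to begin. Patients stopped by telephone before they hold a packet will still start late, but the last-dose date will show which days are missing.
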